7.3 Multicenter Studies

No by-center displays or adjustments for center are planned for this study.

7.4 Multiple Comparisons and Multiplicity

No testing will be performed in this study.

7.5 Planned Subgroups, Interactions, and Covariates

No subgroup analysis is planned.

7.6 Definitions and General Terminology

7.6.1 Baseline

- **Baseline for Ferumoxytol Safety Period**

Baseline for the ferumoxytol period is the last observation before the administration of ferumoxytol.

- **Baseline for MM-398 Safety Period**

Baseline for the MM-398 safety period is the last observation before the first administration of MM-398.

7.6.2 Protocol Deviations

Important Protocol Deviations (IPDs) will be identified and documented for all patients in the safety population prior to database lock based on a review of patient data by sponsor.

The potentially important protocol deviations to be reviewed include, but are not limited to patients who:

1. Receipt of any prohibited therapies as defined in Section 6.5 of the protocol
2. Inclusion/exclusion criteria deviations, unless a waiver was granted
3. Significant deviations in study drug administration

All IPDs will be listed by patient. The number and percentage of patients with IPDs will be summarized by type of deviation and by cohort.

7.6.3 Study Periods

For the evaluation of safety, assessments will be assigned to study periods. These will be:

- Ferumoxytol safety period: from time of the first dose of ferumoxytol to the time of the first dose of MM-398. If an observation contains a date only, then the corresponding ferumoxytol safety period is the time from the date of the first dose of ferumoxytol to the day before the date of the first administration of MM-398. If the patient does not receive MM-398, the ferumoxytol safety period ends at 30 days after the date of the ferumoxytol dose.
- MM-398 safety period: from time of the first dose of MM-398 to 30 days after the date of the last study drug administration of MM-398. If an observation contains a date only, then the corresponding MM-398 safety period begins on the date of the first administration of MM-398.
- Events/observations will be assigned to study periods based on the start date or date and time if time is available.

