2.2.2 Potential Toxicities of Ferumoxytol

The US package insert dated 03/2015 ferumoxytol lists the following warnings and precautions: hypersensitivity reactions, hypotension, iron overload and ability to affect the diagnostic capability of MRI.

Across three randomized clinical trials that enrolled 605 patients treated with ferumoxytol, the following adverse events were reported by $\geq 1\%$ of patients treated with ferumoxytol: nausea, dizziness, hypotension, peripheral edema, headache, edema, vomiting, abdominal pain, chest pain, cough, pruritus, pyrexia, back pain, muscle spasms, dyspnea and rash [17].

Because adverse reactions are reported voluntarily from a population of uncertain size, it is not always possible to reliably estimate their frequency or establish a causal relationship to drug exposure.

In the initial clinical trials of Feraheme (ferumoxytol), conducted predominantly in patients with chronic kidney disease, serious hypersensitivity reactions were reported in 0.2 percent (3/1,726) of patients receiving Feraheme. Other adverse reactions potentially associated with hypersensitivity (e.g., pruritus, rash, urticaria or wheezing) were reported in 3.7 percent (63/1,726) of these patients. In other trials that did not include patients with chronic kidney disease, moderate to severe hypersensitivity reactions, including anaphylaxis, were reported in 2.6 percent (26/1,014) of patients treated with Feraheme.

The following serious adverse reactions have been reported from the post-marketing experience with Feraheme: fatal, life-threatening, and serious anaphylactic-type reactions, cardiac/cardiorespiratory arrest, clinically significant hypotension, syncope, unresponsiveness, loss of consciousness, tachycardia/rhythm abnormalities, angioedema, ischemic myocardial events, congestive heart failure, pulse absent, and cyanosis. These adverse reactions have usually occurred within 30 minutes after the administration of Feraheme. Reactions have occurred following the first dose or subsequent doses of Feraheme.

All IV iron products carry a risk of potentially life-threatening allergic reactions. At the time of the US approval of Feraheme in 2009, this risk was described in the Warnings and Precautions section of the drug label.

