10.7 Safety Analysis

Safety analyses (adverse events and laboratory analyses) will be performed using the safety population. Adverse events will be reported by Sponsor's current MedDRA version. Adverse event coding will be performed to the lowest level term. Frequency and percent summaries will be presented for treatment-emergent adverse events (TEAE) defined as adverse events that occur or worsen in severity following the first dose of MM-398 or ferumoxytol, serious adverse events (SAE), TEAE-related to MM-398 or ferumoxytol and TEAE grade \geq 3, and discontinuation due to TEAE. Adverse events will be summarized by System Organ Class and preferred term. All adverse event data will be listed by patient.

Toxicity grading will be assigned according to NCI CTCAE when possible. Absolute laboratory values will be summarized by visit. Maximum and minimum change from baseline laboratory data will be summarized. Baseline will be the last measurement taken prior to the first study drug administration of MM-398. Frequency and percent of abnormal laboratory values (L/ULN, 2*L/ULN) will be assessed. Shift to most severe toxicity grade will be summarized.

Vital signs will be tabulated for the change from baseline by timepoint. Additional analyses may be performed as described in detail within the SAP.

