6 ANALYSIS POPULATIONS

- **Screened population:** This population includes all patients screened (i.e. who signed the informed consent).
- **Safety population:** This population includes all patients receiving at least one dose of MM-398 or ferumoxytol. If ferumoxytol safety population is different from MM-398 safety population, safety analysis will be performed separately on both populations.

Depending upon patients receiving MM-398 and not ferumoxytol and vice versa, the safety population may be expanded in order to not dilute any adverse event rate:

- Ferumoxytol safety population: any patient receiving ferumoxytol. All analyses using this population will be based on the treatment actually received.
- MM-398 safety population: all patient receiving at least one dose of MM-398. All analysis using this population will be based on the treatment actually received.
- **Efficacy evaluable population**: This population includes all patients receiving at least one dose of MM-398. All statistical analyses of data on non-imaging related efficacy analyses will be performed using efficacy evaluable population.
- **Pharmacodynamic (PD) evaluable population**: This population includes all efficacy evaluable patients with the following: a) pre-treatment FMX-MRI scan(s) and b) radiological scans at 8 weeks. All statistical analyses of data on imaging related efficacy analyses will be performed using PD evaluable population.
- **Pharmacokinetic (PK) population**: This population includes patients receiving at least one dose of MM-398, and blood samples at the predefined timepoints adequately collected (with no major protocol deviations affecting the PK variables & with sufficient number of plasma concentrations to estimate the main PK parameters (C_{max}, AUC)). PK analysis will be documented in a separate SAP.

The term ‘All Screened Patients’ will be used to describe the set of all patients who signed informed consent, including patients who failed screening and any others who initiated screening.

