12 SAFETY ANALYSES

Safety analyses will be based on safety population.

The analysis of safety assessments in this study will include summaries following categories of safety and tolerability data collected for each patient:

- Adverse Events
 - AEs and SAEs
 - AEs leading to discontinuation of study drug
 - TEAE
 - Deaths
- Clinical Laboratory Investigations
- Vital signs
- ECG Investigations
- Pregnancies (if any reported)
- Physical exam

Safety analyses will be presented for each safety population in accordance with the respective study periods (see Section 7.6.3). Safety analyses will be summarized by each cohort and overall for expansion phase.

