12.1 Adverse Events

Adverse events will be coded using the MedDRA dictionary. Levels of classification will include primary system organ class and preferred term. In addition, toxicity grading will be assigned according to NCI CTCAE.

General Rules for summarizing AEs:

- (1) An AE will be considered as treatment-emergent (TE) if it begins on or after study drug dosing, starts prior to dosing and increases in grade/severity or seriousness after dosing, or starts prior to dosing but the causality changed to “related” after dosing. In case of missing dates, an AE will be considered as treatment-emergent.

- (2) In the event of multiple adverse events being reported by the same patient, the most serious causality (related > not related) will be chosen.
- (3) In the event of multiple occurrences of the same adverse events being reported by the same patient, the maximum intensity (Grade 5 > Grade 4 > Grade 3 > Grade 2 > Grade 1 > missing > not applicable) and the most serious causality (related) will be chosen.
- (4) If a patient experiences the same AE (i.e. same preferred term) more than once, they are only counted once under the count for preferred term.
- (5) If a patient experiences more than one AE in a particular system organ class, they will only be included once in the count for the system organ class, but will appear in the count for each appropriate preferred term within the system organ class (unless it is the same preferred term).
- (6) AEs related to study drug tables include only those AEs with a relationship to study drug of 'related' or if there is a missing relationship on the AE page of the CRF.
- (7) For AE severity the following rules will be applied in determining the counts of AEs:
 - An individual patient who experiences two AEs of the same preferred term of the same severity will be included once in the appropriate severity count for the particular AE.
 - An individual patient who experiences two AEs of the same preferred term but different severity will be included once in the severity count for the higher severity but not in the count for the lesser severity.
 - In the total counts for each severity classification, an individual patient who experiences two AEs of different preferred term of the same severity will be included once in the total for the appropriate severity.

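### An adverse event that starts before MM-398 and worsens on it can drop out of the MM-398-period tables, because SAP 7.6.3 assigns events to periods by start date alone

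*SAP*

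**What the plan says.** SAP 7.6.3 defines two periods that follow one another without overlap. The first is given as "Ferumoxytol safety period: from time of the first dose of ferumoxytol to the time of the first dose of MM-398"; the MM-398 period runs "from time of the first dose of MM-398 to 30 days after the date of the last study drug administration of MM-398". The allocation rule is "Events/observations will be assigned to study periods based on the start date or date and time if time is available". Nothing in the section refers to the date on which an event worsens.

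SAP 12 ties the safety output to these periods: "Safety analyses will be presented for each safety population in accordance with the respective study periods (see Section 7.6.3".

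SAP 12.1 rule (1) defines treatment emergence. Besides an AE that begins on or after dosing, it includes one that "starts prior to dosing and increases in grade/severity or seriousness after dosing". Protocol 10.7 takes the same view, defining treatment-emergent events as "adverse events that occur or worsen in severity following the first dose of MM-398 or ferumoxytol". SAP 7.6.1 gives each period its own baseline; for MM-398 it is the last observation before the first MM-398 dose.

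**The concern.** Two rules act on the same event. Rule (1) of SAP 12.1 looks at when the event got worse. SAP 7.6.3 looks only at when it started. For an event that crosses from one period to the next and worsens, they give different answers, and the start-date rule decides which table the event enters.

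The safety profile of MM-398 in the presence of ferumoxytol is a secondary objective (SAP 2.2). The situation is foreseeable:

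- Protocol 6.2.3 lets MM-398 begin once a ferumoxytol reaction has fallen to grade 1, so an event may be ongoing at the first MM-398 dose.
- Protocol 5.2 excludes only diarrhea above grade 1, so a patient may enter with grade 1 diarrhea.
- The ferumoxytol reactions listed in Protocol 2.2.2 include "nausea, dizziness, hypotension, peripheral edema, headache, edema, vomiting, abdominal pain". Nausea, vomiting and abdominal pain also appear among the MM-398 toxicities in Protocol Tables 3 and 4.

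Any error runs in one direction for MM-398: events leave its tables, and none are added.

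**Working it through.** The plan states no figure on this point, so the check is to apply both rules to example records.

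**Inputs.** Period limits and allocation rule: SAP 7.6.3. Treatment-emergent rule: SAP 12.1 rule (1). Maximum interval from ferumoxytol to MM-398: 7 days (Protocol 4.2). Denominators: 10 per cohort and about 30 in the Expansion Phase (SAP 3.1 and 4).

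**Example timeline (illustrative).** Ferumoxytol on day 0, first MM-398 dose on day 7, last dose on day 90. The ferumoxytol period is then day 0 up to day 7, and the MM-398 period is day 7 to day 90 + 30 = 120.

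| Record | Start | Worsens | Period under SAP 7.6.3 | Treatment-emergent relative to MM-398 |
|---|---|---|---|---|
| A. Begins between the two drugs, worsens on MM-398 | day 3 | day 20 | ferumoxytol (0 ≤ 3 < 7) | yes |
| B. Begins before ferumoxytol, worsens on MM-398 | day −5 | day 20 | neither (−5 < 0) | yes |
| C. Begins on MM-398 | day 15 | – | MM-398 | yes |
| D. Worsening entered as a new record | day 20 | – | MM-398 | yes |

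Records C and D cause no conflict. Record A is treatment-emergent for MM-398 but sits in the ferumoxytol tables. Record B is treatment-emergent but enters no period table. The same gap affects ferumoxytol: an event that begins before ferumoxytol and worsens on day 3 is treatment-emergent for ferumoxytol and also falls in neither period.

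**Grade shown.** Rules (3) and (7) of SAP 12.1 choose the highest grade among several occurrences of the same term; they do not govern the grade of a single record. For record A the ferumoxytol table would show the later, higher grade only if the record itself carries its worst grade. Nothing in SAP 7.6.3 or 12.1 limits the grade to the one reached within the period.

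**Size.** One misplaced patient shifts a rate by at most:

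- 1/10 = 10.0 percentage points in one cohort;
- 1/30 = 3.3 percentage points over the Expansion Phase.

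These are upper limits per patient. SAP 12.1 counts a patient once per preferred term, so a second qualifying record of the same term and grade that starts on MM-398 would keep the patient in the count.

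**The case against.** The strongest reply is that the loss depends on a CRF convention the documents do not show. Protocol 9.2 requires worsening after study drug to be recorded, and that can be read as opening a new record with its own onset date. The start-date rule would then place it correctly, as in record D. This stands as a condition on the finding, but it does not remove it. Protocol 9.2 lists one onset date and one resolution date per event and no date of grade change. If worsening always opened a new record, the grade part of the worsening clause in rule (1) would have almost nothing to do.

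Second, SAP 6 says: "If ferumoxytol safety population is different from MM-398 safety population, safety analysis will be performed separately on both populations". If the populations coincide, a table pooled over both periods might be produced, and it would keep the event. SAP 12 carries no such condition, so the text is ambiguous at best.

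Third, the events are not lost from the report. SAP 12.1 lists all AEs by patient. A non-serious condition present before ferumoxytol may also first become a record when it worsens, since Protocol 9.2 starts treatment-emergent reporting at ferumoxytol; but the Protocol Synopsis plans summaries of pre-treatment events, so records like B can exist. The listing of events leading to discontinuation or death is itself arranged by study period (SAP 12.1), so it may inherit the misplacement.

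A reader might infer two stronger things. One is that ferumoxytol is blamed for MM-398 toxicity. The documents do not support that: SAP 12.1 rule (6) builds the drug-related tables from recorded causality, not from the period. The other is that a known share of the serious gastrointestinal events reported in the version 5 amendment rationale would vanish. The documents do not say how many of those events began before MM-398, and diarrhea is not in the ferumoxytol list of Protocol 2.2.2, so no such percentage can be derived.

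**Conclusion.** The point holds in conditional form. SAP 7.6.3, read with SAP 12, conflicts with SAP 12.1 rule (1) for events that begin before MM-398 and worsen on it. If such an event is one record with its original start date, it is missing from the MM-398-period tables, and higher-grade MM-398 toxicity could be understated there.

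The number affected is probably small. The ferumoxytol window is normally no more than 7 days, entry criteria limit existing diarrhea, and the study is descriptive. The denominators are also small, which is why a single patient can matter. The conclusion assumes that the single-record convention applies and that SAP 12 is followed as written. It does not establish that any event will be lost, only that the rules as written allow it.

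**What to change.** Amend SAP 7.6.3 as follows:

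- Assign a treatment-emergent AE to each period in which it starts or increases in grade or seriousness, and tabulate it at the maximum grade reached within that period.
- Where worsening is entered as a new record, use that record's start date.
- Where no date of grade change exists but the event is flagged as worsened after the first MM-398 dose, count it in the MM-398 period at its recorded maximum grade.

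In SAP 12.1 rule (1), apply dosing separately to each drug, judging worsening against the matching period baseline in SAP 7.6.1. State in the SAP which CRF convention was used for worsening events.

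The cost is SAP wording and programming. Rule (1) already requires knowing that an event worsened after dosing, so the flag itself is not a new demand; a grade-change date or a split record is needed to give the exact grade within each period. Some events will appear in both periods, so the two sets of tables should not be added together, and a table footnote should say so.

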7.6.4 Derived and Computed Variables

7.6.4.1 General

When applicable, below derivation rules should be followed:

Time in months: the following will be used to compute time from date 1 to date 2 in months, which will be presented to one decimal place:

$$time\ in\ months = (date2 - date1 + 1) / (365.25 / 12);$$

Age: the number of years since birth to date of informed consent. In SAS, this is computed as:

$$age = floor((intck('month', birthdate, ICdate) - (day(ICdate) < day(birthdate))) / 12);$$

Body temperature in °C: body temperature will be presented in Celsius to one decimal place. Conversion from Fahrenheit is:

$$temperature\ in\ ^\circ C = ([temperature\ in\ ^\circ F] - 32) * (5/9);$$

Weight in kg: weight will be presented in kilograms to one decimal place. Conversion from pounds is:

$$weight\ in\ kg = 0.4536 * \{weight\ in\ lb\};$$

Height in cm: height will be presented in whole centimeters. Conversion from inches is:

$$height\ in\ cm = 2.54 * \{height\ in\ inches\};$$

BMI: body mass index in kg/m², presented to one decimal place:

$$BMI = \{weight\ in\ kg\} / \{height\ in\ cm / 100\}^2;$$

Time since cytological/histo-pathological diagnosis: time from date of first cytological or histo-pathological diagnosis to the date of informed consent in months.

Time since last anticancer therapy: time from date of last dose of most recent prior anticancer therapy to the date of informed consent in months. For example, if PAENDTC is the variable for prior anticancer last dose date:

$$time\ since\ last\ treatment = \{\max(PAENDTC) - date\ of\ informed\ consent\};$$

Time since metastatic diagnosis: time from date of first metastatic diagnosis to the date of informed consent in months.

Time on treatment MM-398: number of days from first treatment to last treatment:

$$\{date\ of\ last\ MM-398\ dose\} - \{date\ of\ first\ MM-398\ dose\} + 1;$$

Dose intensity (mg/m²/week):

$$\{cumulative\ actual\ dose\ in\ mg/m^2\} * 7 / \{days\ of\ exposure\}$$

where days of exposure for MM-398: (date of last study drug administration + 14 - date of first study drug administration)

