7.2.2 Partial and Missing Dates

Missing or partially missing date in the following situations will be imputed for purposes of analysis.

Partial Dates for Death: It is anticipated that nearly all death dates will be completely captured. Any partially missing date of this type will be queried before statistical analyses are performed. In cases of partial dates, death date may be known to month and year. For the primary analysis, date recorded as month and year only will be imputed to the later date of: 1st of the corresponding month and last known alive date plus one day.

Partial/Missing Dates for Study-Related Visits or Procedures: It is anticipated that all study-related visit and procedure dates entered into the clinical study database will be complete (i.e. day, month, year are all recorded) and accurate. Any missing or partially missing date of this type will be queried before statistical analyses are performed. If the day, month, or year is still unknown, then the dates will be imputed as follows for purposes of analysis:

- If the day of the visit or procedure date is missing, then take the previous visit and add the number of days to the next visit according to the visit schedule.
- If the month of the visit or procedure date is missing, then take the previous visit and add the number of months to the next visit according to the visit schedule.
- If the year of the visit or procedure date is missing, then the year will be queried. If the year is unknown, no imputation of year will take place.

Partial/Missing Start Date for Adverse Events or concomitant medications: Missing adverse event (AE) dates will be imputed for the purpose of classification as treatment emergent or not. For any adverse event or concomitant medication that has a missing or incomplete start date, a query will be issued to capture the full date. If only a partial date is reported for the start of an AE or medication, a complete date will be estimated using the following algorithm:

- Completely missing (i.e., missing the year, month and day): the date of first study drug administration. Therefore, any such AE would be treatment emergent, and any such medication would be concomitant.
- Only the year is reported (i.e., missing the month and day): earlier date of '1 January' and the date of first study drug administration.
- The year and month are reported (i.e., missing the day): earlier date of first day of the month and the date of first study drug administration.

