11.3.2.5 Duration of Objective Response (DOR)

DOR is defined as the time from first documentation of response (CR or PR whichever occurs first, by investigator assessment) to the date of disease progression or to death due to any cause, whichever occurs first. Duration of response will be computed only for patients who have CR or PR as best overall response. If progression or death does not occur for a patient with response, the patient's duration of response will be censored in accordance with the rules used for PFS analysis. Duration of objective response will be calculated for all patients that experience documented objective response during the study in weeks as follows:

Duration of DOR (Months) = ((Date of Progression/Death/Censoring - Date of First Recorded CR or PR)+1) *12/365.25

The primary analysis for DOR will be based on the investigator-assessed response. DOR will be summarized by each cohort and overall for expansion phase. The analyses will be performed for efficacy evaluable population.

Imaging - Related:

Pilot Phase:

- **To estimate the correlations between FMX-MRI, TAM levels, and tumor levels of irinotecan and SN-38 with administration of MM-398**
Scatter plot of FMX-MRI vs. tumor SN-38 level, TAM level and irinotecan level will be presented. For FMX-MRI, corrected FMX results across all scanned lesions at the same timepoint for a patient will be used. If there is more than one image data at the same timepoint for a patient, image data will be averaged first before summarizing.
- **To determine the value of FMX-MRI in directing tissue biopsy**
The value of FMX-MRI in directing tissue biopsy will be evaluated by summarizing the feasibility of ferumoxytol (FMX) quantitation in tumor lesions, feasibility of FMX-MRI to identify tumor associated macrophages (TAM), and the relationship assessment between ferumoxytol (FMX) tumor uptake and tumor response.

Expansion Phase

- **To assess the association between deposition, as visualized by ferumoxytol imaging, and measures of efficacy**
The association will be performed on per lesion basis. The analysis will be combined into primary endpoint analysis "The Relationship Between Ferumoxytol (FMX) tumor uptake and tumor response to MM-398" in section 11.1
- **To assess the analytical performance of FMX-MRI measurements and optimize FMX-MRI parameterization**

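### In the SAP, the formula for time since last therapy is reversed and unconverted, a visit-date imputation rule can contradict a recorded month, and the duration-of-response sentence names the wrong unit

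*SAP*

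**What the plan says.** **Time since last therapy (SAP 7.6.4.1).** The section opens with a general rule, "the following will be used to compute time from date 1 to date 2 in months": (date2 - date1 + 1)/(365.25/12). It then defines time since last anticancer therapy as "time from date of last dose of most recent prior anticancer therapy to the date of informed consent in months". The line beneath, introduced as an example, takes the latest prior-therapy end date and subtracts the date of informed consent ("\max(PAENDTC) - date" and onward), with no added day and no division. SAP 9.3 says the variable will be summarized.

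**Partial visit and procedure dates (SAP 7.2.2).** The SAP expects these dates to be complete and queries any gap. If only the day is still unknown, the instruction is: "then take the previous visit and add the number of days to the next visit according to the visit schedule".

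**Duration of response (SAP 11.3.2.5).** The lead-in reads: "Duration of objective response will be calculated for all patients that experience documented objective response during the study in weeks as follows". The formula directly below reads: "Duration of DOR (Months) = ((Date of Progression/Death/Censoring - Date of First Recorded CR or PR)+1) *12/365.25".

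**The concern.** All three are instructions that a programmer is meant to follow, so what they literally return matters.

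The first contradicts the definition beside it in both sign and unit. At stake is one row of the baseline tables.

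The second sets no bound from the part of the date that was recorded. The other partial-date rules in 7.2.2 (death, adverse events, medications, post-study therapy) begin from the recorded month or year, even where they then compare it with another date. The visit rule does not use the recorded components at all. For a disease evaluation, the imputed date would become a progression or censoring date under SAP Table 3, and would carry into duration of response.

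The third states two units for one quantity. Since the SAP uses weeks elsewhere (treatment duration in Section 10, the 24-week stable-disease threshold in 11.3.2.4), a reader cannot tell from the sentence alone which unit is meant.

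**Working it through.** No stated figure in the plan has to be reproduced. Each rule was applied literally to example dates and compared with the SAP's own definitions. All example dates are assumptions.

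**1. Time since last therapy**

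Intended value, from the general rule: (consent - last dose + 1)/(365.25/12), where 365.25/12 = 30.4375. Formula as printed: last dose - consent.

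| Gap, last dose to consent | As printed | General months rule |
|---|---|---|
| 30 days | -30 | 31/30.4375 = +1.0 |
| 60 days | -60 | 61/30.4375 = +2.0 |
| 90 days | -90 | 91/30.4375 = +3.0 |

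Applying the months conversion but keeping the printed order does not repair it: for 60 days, (-60 + 1)/30.4375 = -1.9. The order itself has to change.

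**2. Day missing from a visit or procedure date**

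Inputs: disease evaluation every 8 weeks, +/- 7 days (Protocol 8.2, schedule footnotes); dosing visits +/- 2 days (Protocol 6.1.3). The previous visit is taken to be the previous one of the same type, and the window is centred on the scheduled interval from it.

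- Scan: previous scan 5 January 2017, true scan 27 February 2017 (day 53, inside 56 - 7 = 49), recorded as February 2017 without a day. Rule: 5 January + 56 days = 2 March 2017. The recorded month is overridden, and the date is 3 days late (3/30.4375 = 0.1 month).
- Dosing visit: previous visit 17 January 2017, true visit 1 February 2017 (day 15, inside 14 + 2), recorded as February 2017. Rule: 17 January + 14 days = 31 January 2017. The month is overridden again.

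Taking every previous-visit date in 2016-2017 and weighting each in-window offset equally, the imputed month differs from the true month in:

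- 1,348 of 10,965 combinations (12.3%) for 56 +/- 7 days;
- 144 of 3,655 (3.9%) for 14 +/- 2 days.

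These shares are conditional on a day being missing after a failed query. They are not an expected error rate for the trial. For a scan inside its window, the imputed date is at most 7 days from the true one (7/30.4375 = 0.23 month). The true gap of 49 to 63 days and the imputed gap of 56 days both stay below the 12-week (84-day) limit in SAP Table 3, so this step alone does not carry that scan across the limit.

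**3. Duration of response**

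The formula is (days + 1) x 12/365.25, which is algebraically the general months rule. For 113 inclusive days it gives 113 x 12/365.25 = 3.7 months. The same interval in weeks is 113/7 = 16.1. The formula's label matches what it computes; only the lead-in sentence disagrees.

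**The case against.** **On time since last therapy:** the printed line is only an example showing that the latest end date is to be used, the general months rule heads the same section, and values that are nearly all negative would be noticed. This largely answers the missing conversion. It does not answer the reversed subtraction, because this is the only formula given for the variable and, as shown, the months rule applied in that order still returns a negative value.

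**On imputation:** this is a last-resort convention that applies only when a query has failed, and the SAP does not say that the recorded month is to be discarded. The paired instructions (day missing, add days; month missing, add months) might mean that only the missing component is filled in. The rarity stands, and the documents give no frequency. The component reading does not settle the matter: in the scan example it would keep February but take the day from 2 March, giving 2 February 2017, which is 25 days before the true scan. Under either reading the rule needs a sentence.

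**On duration of response:** the formula is right, correctly labelled, and in the same unit as progression-free survival (SAP 11.3.2.1). That stands in full. A reader might infer that reported durations would be off by a factor of 365.25/12/7 = 4.35. The documents do not support that. The factor arises only if the formula's output is relabelled as weeks against its own label.

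It is also fair to say that the study is descriptive with no formal testing (SAP Section 4), so no decision or sample size depends on these rules.

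**Conclusion.** The point holds as three defects of unequal weight, all minor.

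- The time-since-last-therapy formula is wrong as written: negative and in days whenever the last dose precedes consent (-60 against +2.0 months for an assumed 60-day gap). The effect is confined to a descriptive baseline summary.
- The visit-date rule can contradict a recorded month. Within the protocol's scan window the displacement is at most 7 days, assuming that the interval runs from the previous scan. How often it would arise is not known from the documents.
- The duration-of-response sentence is a unit inconsistency. No wrong value follows from using the formula.

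A reader might conclude that all three rules produce wrong values. Only the first does so routinely. The second does so conditionally, and the third does not.

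**What to change.** Three wording edits to the SAP, with no change to data collection or design:

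1. In 7.6.4.1, replace the example formula with (date of informed consent - max(PAENDTC) + 1)/(365.25/12).
2. In 7.2.2, add that when only the day is missing, the imputed visit or procedure date must stay within the recorded month and year. One workable convention is the day in that month nearest to the scheduled date. In the scan example this gives 28 February 2017, one day from the true date. Other conventions would also serve, provided that one is stated.
3. In 11.3.2.5, change weeks to months in the lead-in sentence and leave the formula as it is.
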